6.1. Study Design

Patients receiving aRCC treatment (see [Table 4](#)), between April 2018 and the present, who have no prior aRCC treatment in their claims history will be identified for this study. The index date for each analysis will be defined as the date of initiation of the aRCC treatment. Patients must have at least 2 RCC diagnoses at least 30 days apart to be included. Patients must also have 2 secondary malignancy ICD9 or ICD10 codes (often used in claims data to suggest cancer metastases) at least 30 days apart in the 12 months pre and one month post index aRCC treatment. [CCI](#)

Various algorithms and temporal relationships between the secondary malignancy codes, RCC diagnosis codes and other cancer codes were explored toward developing the criteria for metastatic advanced RCC for this study.

Study will require a minimum of 12 months of enrollment prior to the index date. Feasibility was assessed for various lengths of continuous enrollment criteria (3, 6 and 12 months post index date) toward understanding sample sizes available for analysis and follow-up periods. Study outcomes will be assessed for three patient cohorts (3, 6 and 12 month cohorts) according to their available months of continuous enrollment.

PFIZER CONFIDENTIAL

First line therapy cohorts will first be presented for all patients regardless of follow-up time available. Baseline characteristics, costs and utilization will be measured over the 6 months prior to the index date. Duration of therapy and utilization analysis will require at least 6 months of post-index enrollment, with sub-analysis preformed on the cohorts with 3-months and 12-months of post-index enrollment. Utilization and cost will be performed per-utilizer-per-month (PUPM), and then separately for each of the cohorts with 3-month, 6-month and 12-months of post-index enrollment.

The analysis will focus on, but is not limited to, the following regimens:

- a. **Combo IO:** nivolumab combined with ipilimumab;
- b. **Monotherapy TKI:** sunitinib, cabozantinib, and pazopanib;
- c. **Combo TKI + IO:** avelumab in combination with axitinib, pembrolizumab in combination with axitinib;
- d. **Other:** all others regimens.

PFIZER CONFIDENTIAL

[figure not shown]
[figure not shown]
[figure not shown]

Figure 1: Cohort Identification

Analysis 1. Treatment Patterns and Duration

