Treated Period Follow-Up. Patients will be followed over the period treated with advanced RCC therapy. Time treated will be defined as the time from the index date to the date of the end of the last advanced metastatic RCC prescription (end of supply for orals/administration date plus 30 days for injectables), end of enrollment, end of follow up, or death (see more specifics on oral versus injectable rules in [6.3.1 Variables](#) section of this protocol).

Analysis 2. Describe various treated populations of interest by demographics, clinical characteristics, as well as cost and utilization

Describe the demographics and other baseline characteristics of the first-line treated cohorts of interest identified in the treatment patterns analysis (Analysis 1) for RCC patient as follows:

Baseline Characteristics (see [6.3.2 Baseline Characteristics](#)):

- Age at index;
- Gender;
- Race;
- Region;

PFIZER CONFIDENTIAL

- Payor;
- Clinical characteristics: Quan-Charlson Comorbidity Index (CCI) scores and baseline comorbidities;
- Prior treatment (6 months prior) - nephrectomy, radiation/ablation, interferon, high-dose interleukin-2, other anti-neoplastic medications;
- Secondary malignancy locations (6 months prior);
- Baseline costs of care (6 months prior);
- Baseline health care resource utilization (6 months prior).

Analysis 3: Evaluate the key outcomes of interest for advanced RCC therapy regimens toward demonstrating existing unmet needs in RCC given currently available therapies (eg, ipilimumab/nivolumab).

Treatment duration, discontinuation, interruption, switching and therapy augmentation will be presented, as will the burden of disease costs and health care utilization. Survival will also be explored, although regimens are too new for extensive follow-up time.

Overall Outcomes Study Period. For the outcomes analysis, follow-up will be defined as the time from the index date to the end of specified follow up period of 6 months, end of enrollment, or death. Follow-up may vary given sample sizes of study population, with by subanalysis using 1-year or 2-years of follow-up time from study index date for certain sub-populations.

Outcomes include:

- **Time to Treatment Failure (TTF)** – First line time to treatment failure (TTF) is defined as the time from first-line therapy start to treatment discontinuation for any reason, including switched, augmented therapy, end of enrollment, death.

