- **% continuing** – those with no gap in therapy greater than 30 days and who do not begin a new treatment during the study period.
- **% discontinuing** – those with gap in therapy greater than 30 days and who do not begin a new treatment.
- **% with treatment interruption** - those with gap in therapy greater than 30 days but who eventually continue the original treatment (have an additional administration or refill) and do not switch or augment therapy during the study period.
- **% switching** – those with gap in therapy greater than 30 days and who begin a new treatment.
- **% augmenting** – those who begin a new treatment but continue using the original treatment (have an additional administration or refill) and do not have a gap in therapy greater than 30 days of their original treatment.
- **Overall and aRCC Follow-Up Costs:** Total and RCC-specific pharmacy, medical costs from aRCC therapy index through follow-up period (costs summarized as: mean, median costs per patient and costs per patient per month).

PFIZER CONFIDENTIAL

- **Overall and aRCC Follow-Up Utilization:** Total and RCC-specific inpatient, ER, outpatient visits from aRCC therapy index through follow-up period (utilization will be summarized as: mean, median utilization per patient and utilization per patient per month).
- **Overall landmark survival:** Using Optum claims and PanTher data, landmark survival will be described and compared over follow-up time periods (3, 6, 12 months).
- **Mean/Median Survival:** Using Optum claims and PanTher data median survival time will be described and compared over follow-up time periods determined after feasibility assessments of cohorts of interest.

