6.2.1. Inclusion Criteria

Subjects will be selected irrespective of their survival status. Patients must meet all of the following inclusion criteria to be eligible for inclusion in the study:

- **Index date:** The first prescription or administration of one of the medications indicated for advanced RCC recorded in the database between April 2018-March 31, 2019, among those with no aRCC treatment in their history.
- Age 18 years or older in the year of the index first line therapy prescription.
- 2 or more RCC diagnoses (ICD-9: 189.0; ICD-10: C64.1, C64.2, C64.9) at least 30 days apart, in the 1 year prior to the index date until 30 days post index date.

PFIZER CONFIDENTIAL

- 2 or more code for secondary malignancy codes indicating possible diagnoses for metastatic disease at least 30 days apart, in the 1 year prior to the index date until 30 days post index date. (ICD-9: xx-199.xx; ICD-10: C77-C79, except ICD9: 198.0 Secondary malignant neoplasm of the kidney and ICD10: C79.0 Secondary malignant neoplasm of the kidney and renal pelvis).
 - CCI [REDACTED]
- Continuous enrollment from 12 months prior to the index date. Patients will be required to have continuous enrollment from their index date until the end of the available data. This will allow for sub-analysis of cohorts with 3 months, 6 months and 12 months of available data.

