6.3.2. Baseline Variables

Table 6. Baseline Variables

[figure not shown]
Variable	Operational definition
Baseline demographics	
Index Date	Date of first RCC diagnosis on record
Index Year	Index year for the patient
Age	Continuous: Years Patient age at index date
Sex	Categorical: Male or female
Insurance Coverage	Categorical: Commercial, Medicare, or Medicaid
US Region	Categorical: Northeast, Midwest, South, West
Race	Categorical: based on each database
Clinical characteristics	
Time to systemic therapy <1 year	From IMDC: <1 year from time of diagnosis to systemic therapy
NCI Charlson comorbidity index (DCI)	Categorical: 0, 1-2, 3+
History of smoking	Categorical: Yes/No Prior history of smoking – record of smoking cessation medication or V code.
History of systemic therapy	Categorical: Yes/No A record of being given certain systemic drugs (interferon, interleukin 2, gemcitabine and doxorubicin)
History of surgical resection	Categorical: Yes/No History of nephron sparing or radical nephrectomy. ICD-10-CM Z90.5/ICD-9-CM V45.73 Acquired absence of kidney.

PFIZER CONFIDENTIAL

Variable	Operational definition
History of radiation therapy	
Categorical: Yes/No
 
ICD-10-CM Z51.0/ICD-9-CM V58.0 Encounter for radiotherapy.
 
ICD-10-PCS › D › Urinary System:
 
• DT0 Beam Radiation;• DT1 Brachytherapy;• DT2 Stereotactic Radiosurgery;• DTY Other Radiation. 
CPT Codes:
 
77401 Radiation treatment delivery, superficial and/or ortho voltage, per day;
 
77402 Radiation treatment delivery, >1MeV; simple;
 
77407 intermediate;
 
77412 complex.
 
New Codes
 
77085 Dual-energy x-ray absorptiometry (DXA), bone density study, 1 or more sites; axial skeleton (eg, hips, pelvis, spine), including vertebral fracture assessment.
 
77086 Vertebral fracture assessment via dual energy X-ray absorptiometry (DXA).
 
77306 Teletherapy isodose plan; simple (1 or 2 unmodified ports directed to a single area of interest), includes basic dosimetry calculation(s).

PFIZER CONFIDENTIAL

[figure not shown]

Variable	Operational definition

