6.3.3. Outcomes Variables

Table 7. Outcomes Variables

Variable	Operational definition
Days to Treatment Failure (TTF)	Time to treatment failure (TTF) is defined as the time from therapy start to treatment discontinuation for any reason, including switched, augmented therapy, end of enrollment, death.
Discontinuation	% discontinuing – those with gap in therapy greater than 30 days and who do not begin a new treatment.
Switching	% switching – those with gap in therapy greater than 30 days and who begin a new treatment.
Augmentation	% augmenting – those who begin a new treatment but continue using the original treatment (have an additional administration or refill) and do not have a gap in therapy greater than 30 days of their original treatment.
% Survived 3,6, 12 months	Mean/Median Survival Time (Days): Survival time will be described over 3,6, 12 months given follow-up time available in the data. Overall survival is defined as the length of time from index date of RCC diagnosis to patient death (or index date associated with FL Tx?) or end of available data for with no death indication. Overall landmark survival: described and compared over follow-up time periods (3,6, 12 months). Percentage of patients alive at 3,6, 12 months.
Overall Survival Time	Continuous: days Overall survival is defined as the length of time from index date of RCC diagnosis to patient death (or index date associated with FL Tx?)

PFIZER CONFIDENTIAL

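### The index date is defined two ways and Table 7 leaves the survival time origin as an open question; starting the clock at diagnosis would count the wait for treatment as guaranteed survival

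*Combined protocol and SAP*

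**What the plan says.** Section 6.1 is explicit: "The index date for each analysis will be defined as the date of initiation of the aRCC treatment". Section 6.2.1 agrees, taking as index "The first prescription or administration of one of the medications indicated for advanced RCC" in the accrual window. Under Analysis 3 in Section 6.1, "follow-up will be defined as the time from the index date to the end of specified follow up period of 6 months", or to end of enrollment or death, and "landmark survival will be described and compared over follow-up time periods (3, 6, 12 months").

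Table 6 (Section 6.3.2) gives a different definition of Index Date: "Date of first RCC diagnosis on record". The same table defines age as "Patient age at index date" and includes an IMDC item, "<1 year from time of diagnosis to systemic therapy".

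Table 7 (Section 6.3.3) reads: "Overall survival is defined as the length of time from index date of RCC diagnosis to patient death (or index date associated with FL Tx". In the document the bracket closes with a question mark. The sentence appears both in the row for the percentage surviving 3, 6 and 12 months and in the row for overall survival time.

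Section 6.7 plans Kaplan-Meier curves for survival, does not mention delayed entry, and states that no separate SAP is required.

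**The concern.** The two index dates differ for any patient diagnosed before treatment. The Table 7 bracket is a drafting query left inside an operational definition, so the outcome has no fixed time zero. Two analysts working from this text could choose different origins. Read literally, Table 6 also moves age at index to diagnosis.

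The choice matters because cohort entry depends on starting treatment. A patient who died between diagnosis and treatment can never be included. If time zero is diagnosis and everyone is treated as at risk from that day, the interval carries no deaths by construction. Landmark percentages and median survival are then too high. If the interval differs between first-line regimens, cohorts with the same survival after treatment will look different.

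**Working it through.** **Which origin each place uses**

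| Place | Origin |
|---|---|
| 6.1, index date | treatment start |
| 6.2.1, index date | treatment start |
| 6.1, Analysis 3 follow-up | index date, hence treatment start |
| Table 7, time to treatment failure | therapy start |
| Table 8, costs and RCC-specific utilization | therapy index |
| Table 6, Index Date | first RCC diagnosis |
| Table 7, both survival rows | RCC diagnosis, with treatment start as a query |

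Most of the protocol points to treatment start. Tables 6 and 7 are the exceptions, and they hold the variable-level definitions a programmer would use.

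**Range of the diagnosis-to-treatment lag.** Section 6.2.1 requires two RCC codes at least 30 days apart, both between one year before and 30 days after treatment start. The later code can fall no later than day +30, so the earlier falls no later than 30 − 30 = day 0. The lag is never negative, and it can be zero. It has no stated upper limit, because Table 6 takes the first diagnosis on record, and the IMDC item there splits at 1 year.

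**Effect on landmark survival.** The plan gives no survival figure to reproduce. Inputs assumed for illustration: exponential survival from treatment with median m months, and a fixed lag of L months independent of survival. Measured from diagnosis without delayed entry,

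S(t) = 1 if t ≤ L, otherwise 0.5^((t − L)/m).

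Example: m = 24, t = 12, L = 6 gives 0.5^(6/24) = 84.1%; L = 0 gives 0.5^(12/24) = 70.7%.

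12-month survival from diagnosis:

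| Median from treatment | L = 0 | 1 | 3 | 6 | 12 or more |
|---|---|---|---|---|---|
| 12 months | 50.0% | 53.0% | 59.5% | 70.7% | 100% |
| 24 months | 70.7% | 72.8% | 77.1% | 84.1% | 100% |
| 36 months | 79.4% | 80.9% | 84.1% | 89.1% | 100% |

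At the 6-month landmark with m = 24, lags of 0, 1, 3 and 6 months give 84.1%, 86.6%, 91.7% and 100%. The median becomes m + L, for example 24 + 6 = 30 months.

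**Two regimens with the same survival from treatment.** With lags of 1 and 6 months, the false 12-month difference is 84.1 − 72.8 = 11.3 points for m = 24, 70.7 − 53.0 = 17.7 points for m = 12, and 89.1 − 80.9 = 8.2 points for m = 36.

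**Varying and dependent lag.** Let the lag be exponential with median 6 months, and m = 24. Under independence the lag rate is four times the death rate, so 12-month survival from diagnosis is (4/3) × 0.5^(12/24) − (1/3) × 0.5^(12/6) = 0.9428 − 0.0833 = 85.9%. Independence is doubtful, since Table 6 lists the lag as a prognostic item. Simulating dependence with a Gaussian copula (3 million draws) gives 89.9%, 82.6% and 80.6% for copula parameters −0.3, 0.3 and 0.5. All exceed 70.7%.

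**The case against.** The strongest reply is that the bias is conditional. Section 6.1 fixes the index at treatment for every analysis, and the Table 7 query itself offers that option. A sensible analyst may well choose it, and Section 6.8 requires a programming plan and checking by a second data scientist. That is fair, but neither step says which origin to use, and the variable-level text names diagnosis first.

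Several narrower points stand:

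- The statement that survival will be compared refers to follow-up periods and names no regimen contrast. Section 5 does describe outcomes by first-line cohort, and Section 6.7 plans standardized differences, so readers could make that contrast. No document figure shows that lags differ by regimen.
- The exclusion in Section 6.2.2 for under 3 months of post-index data is garbled. If it removes early deaths, every landmark shifts. With m = 24, 12-month survival from treatment becomes 0.5^(9/24) = 77.1%, and lags of 1 and 6 months give 0.5^(8/24) = 79.4% and 0.5^(3/24) = 91.7%, a 12.3-point gap. The direction is unchanged.
- Only one of the two Table 7 survival rows states a censoring rule.
- Section 5 limits survival to Optum Clininformatics, while Section 6.1 adds PanTher, so how far the analysis will be replicated is itself unclear.
- Survival is exploratory in a descriptive study that disclaims causal inference.

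These points limit the claimed size and reach. They do not supply the missing time zero.

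**Conclusion.** The concern holds. The contradiction on index date and the undecided survival origin are certain from the text and need no assumption. The guaranteed survival time follows if the diagnosis wording is used with ordinary Kaplan-Meier curves. A patient diagnosed 12 months or more before treatment would then pass all three landmarks by construction.

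The size cannot be taken from the documents. Under the assumed 24-month median, a 3- to 6-month lag adds about 6 to 13 points to 12-month survival (77.1 − 70.7 = 6.4; 84.1 − 70.7 = 13.4). These figures rest on exponential survival, a fixed and independent lag, and no early-death exclusion. The upward direction persisted in the dependence settings examined. Although survival is exploratory, it is a listed outcome and cannot be programmed reproducibly as written, so this should be settled before analysis starts.

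**What to change.** Make three wording edits:

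1. In Table 6, define Index Date as the date of the first prescription or administration of a Table 4 medication, matching Sections 6.1 and 6.2.1.
2. In the Table 7 row for percentage surviving, measure survival from that date and delete both the diagnosis origin and the bracketed query.
3. Make the same change in the Table 7 row for overall survival time.

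The change of origin does not require altering the censoring at end of available data in the percentage-surviving row. The overall survival time row has no such rule, so state one there in the same edit and reconcile it with the follow-up end points in Section 6.1.

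Keep time to first-line treatment as the separate descriptive variable in Table 5. If survival from diagnosis is also wanted, present it as a separately labelled analysis with delayed entry (left truncation) at treatment start.

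The cost is a few lines of text and no new data. Reported survival may look less favourable than with a diagnosis origin. The edits do not resolve any conditioning on survival from the 3-month exclusion in Section 6.2.2, which needs its own clarification.

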6.3.4. Cost and Utilization Variables

[figure not shown]
Table 8. Cost and Utilization Variables

Variable	Operational definition

All-cause Health Resource Utilization: Total inpatient, ER, outpatient visits from index aROC period.
	
Any healthcare resource use per patient per month (PPPM) will be examined for each regimen-based cohort under each LOT and will further be categorized as the following:
 
Occurrence of (Categorical: Yes/No):
 
• any inpatient stay;• any outpatient visit;• any ER visit. 
Number of visits (Continuous):
 
• inpatient stays;• outpatient visits;• ER visits. 
Inpatient LOS (Continuous: days).

PFIZER CONFIDENTIAL

Variable	Operational definition

aRCC HR Utilization:
 
RCC-specific inpatient, ER, outpatient visits from aRCC therapy index through follow-up period.
	
RCC-related healthcare resource use per patient per month (PPPM) will be examined for each regimen-based under each LOT.
 
Medical claims will be considered RCC-related if they have an ICD-9/10-CM diagnosis code for RCC in any position on the claim.
 
Occurrence of (Categorical: Yes/No):
 
• any inpatient stay;• any outpatient visit;• any ER visit. 
Number of visits (Continuous):
 
• inpatient stays;• outpatient visits;• ER visits. 
Inpatient LOS (Continuous: days).

PFIZER CONFIDENTIAL

Variable	Operational definition
All-cause Healthcare Costs Overall medical costs and pharmacy costs from aRCC therapy index through follow-up.	
Continuous: dollars
 
All-cause healthcare costs will be examined for each regimen-based cohort under each LOT. Costs will be adjusted to 2019 US dollars (USD) using the medical care component of the Consumer Price Index (CPI). Health care costs PPPM will be provided, and will be further categorized as:
 
• Inpatient stay costs;• Outpatient costs;• ER visit costs;• Pharmacy costs (medical);• Pharmacy costs (pharmacy);• Total costs.
mRCC-related Healthcare Costs RCC-specific pharmacy, medical costs from aRCC therapy index through follow-up period	
Continuous: dollars
 
aRCC therapy Pharmacy claims for medication used to treat RCC will be included in the pharmacy costs using pharmacy claim data.
 
RCC-related healthcare costs will be examined for each regimen-based cohort under each LOT. Costs will be adjusted to 2019 US dollars (USD) using the medical care component of the Consumer Price Index. Health care costs PPPM will be provided, and will be further categorized as:
 
• Inpatient stay costs;• Outpatient costs;• ER visit costs;• Pharmacy costs (medical claims);• Pharmacy costs (pharmacy claims);• Total costs (total pharmacy + total medical).

PFIZER CONFIDENTIAL

6.4. Data Sources

Results will be replicated to the extent possible across various real world databases in order to confirming and validate results across data sources. At the start of the study, four databases will be evaluated. IBM's Truven MarketScan Commercial, Optum Clininformatics, the IMS PharMetrics claims databases and The PanTher (which has both Humedica EMR data including EMR notes linked to Optum claims). After population sizes are assessed in the various databases, sub-analysis for populations with adequate patient data will be clarified in an amendment to this protocol.

[figure not shown]
Optum Clininformatics:

Optum Clininformatics has access to a proprietary research database containing claims and enrollment data dating back to 1993 with the opportunity to link patient and physician survey data to pharmacy and medical claims, medical record data, socioeconomic measures, and clinical laboratory results on over 123 million lives. Underlying information is geographically diverse across the United States, and is updated frequently. The research activities utilize de-identified data from the research database except in limited instances where applicable law allows the use of patient identifiable data.

Claims for pharmacy services are typically submitted electronically by the pharmacy at the time prescriptions are filled. The claims history is a profile of all outpatient prescription pharmacy services provided and covered by the health plan. Pharmacy claims data include drug name, dosage form, drug strength, fill date, days of supply, financial information, and de-identified patient and prescriber codes, allowing for longitudinal tracking of medication refill patterns and changes in medications. Pharmacy claims are typically added to the research database within 6 weeks of dispensing.

Medical claims or encounter data are collected from all available health care sites (inpatient hospital, outpatient hospital, emergency room, physician's office, surgery center, etc.) for virtually all types of provided services, including specialty, preventive and office-based treatments. Medical claims and coding conform to insurance industry standards. Claims for ambulatory services submitted by individual providers, eg, physicians, use the HCFA-1500 format. Claims for facility services submitted by institutions, eg, hospitals, use the UB-82 or UB-92 format. Medical claims include: multiple diagnosis codes recorded with the ICD-9-CM diagnosis codes; procedures recorded with ICD-9-CM procedure codes, Current Procedural Terminology (CPT), or Health Care Financing Agency (HCFA) Common Procedure Coding System (HCPCS) codes; site of service codes; provider specialty codes; revenue codes (for facilities); paid amounts; and other information. Typically, facility claims do not include any drugs administered in hospital. Approximately 6-9 months following the delivery of services is required for complete medical data, therefore patients will be followed for this additional time period. In summary, the analysis window will include data from 24 months pre index date, and 24 months post index date.

PFIZER CONFIDENTIAL

Integrated Optum E.H.R and Claims (PanTher)

Integrated Optum E.H.R. (formerly Humedica) clinical data and Optum Clininformatics administrative claims data (United enrollees) are included in the Optum PanTher Database. Estimated to be approximately 15% of the Optum Claims lives are represented in this database. This asset combines the clinical specificity of the Optum E.H.R. data with the administrative claims data which includes cost data, pharmacy fill data, and enrollment time periods among other things.

The Optum EHR database has broad geographic representation and includes patient demographic and clinical information, including diagnosis, medications, labs, procedures, microbiology and biomarkers. Optum EHR also extracts data from physician notes using industry-leading Natural Language Processing (NLP).

[figure not shown]
The Optum EHR database includes patient records from multiple EMR systems which capture data from different sites of care and a full spectrum of inpatient and outpatient treatment (eg, both Written Prescription and Inpatient-Administered medications). Records are completely de-identified and are fully compliant with the Health Insurance Portability and Accountability Act (HIPAA). Data is sourced from large Integrated Delivery Networks (IDN) with over 60% of patients having both outpatient and hospital information. The remainder of the patients are from large multi-specialty physician practices.

Outpatient laboratory test results are available for subpopulations of the research database. Standard Logical Observation Identifiers Names and Codes (LOINC) coding is used to define specific tests and results. Test results data can be linked to the other health care utilization and pharmacy claims data in the research database. Results included in the database are typically from blood-based tests (eg, low-density lipoprotein, glycated hemoglobin levels) that are sent for processing to two of the largest laboratory facilities in the country. Data are available for approximately 30-40% of members who were administered the test, depending on the test.

Truven Marketscan Commercial:

The MarketScan data warehouse is a family of databases from commercially insured lives. Pfizer licenses the following data sources: healthcare claims, hospital drug/discharge information with links to claims data and Medicare Supplemental files. The Truven Health MarketScan Research Databases reflects the combined healthcare service use of individuals covered by Truven Health clients (including employers, health plans, and hospitals) nationwide. Truven Health builds databases comprise the healthcare experience of the clients' covered populations, as well as information about the populations themselves and the providers that serve them. MarketScan Research Databases provide detailed cost, utilization, and outcomes data for healthcare services performed in both inpatient and outpatient settings. In the claims databases, the medical services are linked to outpatient prescription drug claims and person-level enrollment data using unique enrollee identifiers.

PFIZER CONFIDENTIAL

The MarketScan Commercial Database contains the healthcare experience of privately insured individuals. Coverage is provided under a variety of fee-for-service, fully capitated, and partially capitated health plans, including preferred provider organizations, point of service plans, indemnity plans, and health maintenance organizations.

The Enrollment Detail Table provides a single record per month of enrollment for each enrollee, with detailed demographic information.

Claims are not included in the database until they have been adjudicated; there is a lag of approximately six months after the close of a calendar year or a quarter between services provided and their inclusion in the Research Databases. However, the Early View Database has a 90-day lag that includes paid amounts for 100 percent of prescription drugs, approximately 85 percent of physician office visits, and approximately 70 percent of hospital claims. The MarketScan Early View Database includes all of the components found in the standard MarketScan Commercial and Medicare Supplemental Databases. It includes standardized inpatient, outpatient, pharmaceutical, and health-plan enrollment data. The MarketScan Early View Database captures healthcare services incurred up to 90 days before data release and includes only adjudicated claims. However, the medical component of care for some patients will not be complete, since some claims (particularly inpatient claims) take longer to be adjudicated. Because this study is examining only comorbidities prior to and treatments during or prior to glasdegib initiation fully adjudicated claims are not required and all available data will be used including Commercial, Medicare Supplemental, and Early View Databases.

[figure not shown]
Pharmetrics Plus

The PharMetrics Plus database is comprised of fully adjudicated medical and pharmacy claims. Specifically, it contains a longitudinal view of inpatient and outpatient services, prescription and office/outpatient administered drugs, costs and enrollment information. With PharMetrics Plus, you can track an enrolled patient across all sites of care: hospital, specialist, emergency room, pharmacy, primary care, ambulatory, and more.

There are over 140 million unique enrollees with both medical and pharmacy benefits. The enrollee population in the PharMetrics Plus database is generally representative of the under 65 commercially insured population in the US with respect to both age and gender. We have over 10 million enrollees who are over 65 years of age. Longitudinal enrollment range of individuals in the database on average is 36 months and more than 42 million patients have 3 or more years of continuous enrollment.

The PharMetrics Plus database offers a diverse representation of payer types, provider specialties, geographic granularity and linking capabilities. Patient region and state are standard patient variables and zip3 is optional and available for a subset of patients. Provider identification is an optional variable and available for a subset of providers using the National Provider Identifier. Patient linking is achieved by leveraging IQVIA's patented

PFIZER CONFIDENTIAL

technology for the subset of patients assigned a unique, encrypted patient key in multiple databases. Please note that there can be limits to the provisioning of the combination of some variables when linking is enabled.

Commercial insurance is the most frequent plan type captured for the enrollee population but other types are also found, including Commercial Medicare, Commercial Medicaid, Self-Insured, Indemnity and Others. In addition to standard fields such as inpatient and outpatient diagnoses and procedures, retail and mail order prescription records, PharMetrics Plus has detailed information on the pharmacy and medical benefit (copayment, deductible), the inpatient stay and provider details (provider specialty included in all extracts). Economic variables include the negotiated rate between the plan and providers (allowed) and the actual amount paid by health plans to the provider for all services rendered. Charge amount is also available for a subset of claims. Other data elements include dates of service, demographic variables (age, gender, and geographic region), product type (eg, HMO, PPO), payer type (eg, commercial), and start and stop dates of health plan enrollment. All data are HIPAA compliant to protect patient privacy.

While the most recent release of the PharMetrics Plus database is typically used to create all client deliverables, there may be a 4-6 month lag with newer claims largely owing to the typical processing time for claims adjudication mentioned above.

